Table 1. Summary of Weekly Study Assessments

Assessments	0	1	2	3	4	5	6	7	8	9	10	11	12	13	14	25
SCID I	x															
TLFB	x	x	x	x	x	x	x	x	x	x	x	x	x	x	x	x
OCDS		x	x	x	x	x	x	x	x	x	x	x	x	x	x	x

ADS	x														
Demographics	x														
CIWA	x														
CAPS Dx	x														
CAPS Sx		x		x		x		x		x		x		x	x
HAMD		x	x	x	x	x	x	x	x	x	x	x	x	x	x
PCL-C		x	x	x	x	x	x	x	x	x	x	x	x	x	x
SAFTEE		x	x	x	x	x	x	x	x	x	x	x	x	x	x
Independent Psychiatric Exam	x														
Physical Examination	x														
Medication Count		x	x	x	x	x	x	x	x	x	x	x	x	x	x
EKG	x														
Medical History	x														
Labs	x				x			x				x			x
UTOX	x	x	x	x	x	x	x	x	x	x	x	x	x	x	x

Data Analysis:

Descriptive statistics and graphs will be used to summarize the data on all randomized veterans. All continuous variables will be examined for adherence to the normal distribution using normal probability plots and Kolmogorov-Smirnov tests. Transformations will be applied if needed. If normality is not satisfied and transformations do not help with achieving normality alternative analytic strategies will be considered such as generalized estimating equations (GEE) or nonparametric methods for repeated measures analysis (Brunner et al 2002). For the primary hypotheses we will use mixed effects models to assess change in alcohol consumption and craving over time. Study medication (zonisamide vs placebo) and time (in weeks and months) will be used as a within-subject factors. The primary outcome drinking variable will be heavy drinking days and drinks per week calculated from the timeline data.

If significant differences between groups are observed Bonferroni adjusted post-hoc tests will be performed to test group differences at each time point. The same model will be used to examine changes in craving (using the OCDS) and PTSD symptoms (using the PCL every week and the CAPS every two weeks) over time.

XII. Labeling and Storage of Data and Specimens

All data and blood specimens will be stored without direct identifiable information, but will be identifiable via a linking code. Blood will not be used for the purpose of establishing cell lines. Any hard copy records associated with the study will be kept in locked offices. The secured research records are labeled with code numbers only (names and other identifying information are kept separate from research records). Access to hard copy data is only given to

staff members working on the study. Only staff members designated to handle or analyze study samples will have access to the samples and their storage. Coded blood samples are stored in clinic-specific refrigerators and freezers, which are located in secure rooms. As per routine all electronic files (e.g., database, spreadsheet) will be password protected. Any computer hosting such files will have a BIOS password to prevent access by un-authorized users. Furthermore, for systems not running Windows 2000/XP, a password-protected screen saver will be installed and configured to activate ten minutes after the computer has been idle.

XIII. Risk and Injury

Zonisamide

Zonisamide is approved for the adjunctive treatment of partial seizures in adults with epilepsy. Zonisamide has shown efficacy or potential efficacy in treating bipolar depression or subtypes of bipolar disorder (Anand et al 2005; Baldassano et al 2004; Ghaemi et al 2006; Kanba et al 1994; McElroy et al 2005; McIntyre et al 2002), and demonstrated efficacy in weight reduction in overweight individuals, and potential efficacy in the treatment of binge eating (Gadde et al 2003; Li et al 2005; McElroy et al 2004). It has been used as a potential treatment for alcohol use in several clinical trials, including our pilot study. The usual dose across studies is 200-400 mg. Studies suggest zonisamide is effective at 400 mg - a large ongoing clinical trial (clinicaltrials.gov) is also using 400 mg. Although in our pilot study the dose was 500mg we chose a dose of 400mg given that this study is conducted in veterans with comorbidity, and the goal is to allow subjects to also participate in E-CPT-C.

The most common adverse events observed in clinical studies (that were more common than placebo) were: fatigue (17% vs. 7% for placebo), decreased appetite (13% vs. 6%), dizziness (13% vs. 7%), headache (10% vs. 8%), nausea (9% vs. 6%), and agitation/irritability (9% vs. 4%). Although psychosis occurred at a rate of approximately 2% in trials involving patients with a seizure disorder, this was likely related to the patients' seizure disorder. There were no reports of psychosis in a trial of zonisamide for obesity. Rare or less common effects associated with zonisamide include a sensation of numbness, tingling, or prickling in parts of the body (less than 1%), a distorted sense of taste (2% vs. 0%) difficulty concentrating or remembering (4% vs. 0%), vomiting (3% vs. 0%), and trouble sleeping (3% vs. 0%). Less common, but not rare, side effects include kidney stones, which were reported in 4% of epilepsy patients taking zonisamide in combination with another anti-seizure medication in clinical trials. No kidney stones were reported during a small trial of zonisamide in the treatment of alcohol problems. Drinking an adequate amount of fluids is recommended while taking zonisamide. This may reduce the risk of kidney stones. Rare but potentially serious reactions that occurred more often than with placebo in epilepsy trials were hematologic reactions such as aplastic anemia, and severe allergic or toxic reactions. There are anecdotal reports of zonisamide worsening mood symptoms in psychiatric patients, including those with bipolar disorder. Therefore, we will monitor symptoms frequently and closely in this pilot project.

Sometimes zonisamide may cause a condition known as "metabolic acidosis" in some patients, which is a dangerous change in the acid and base balance of the blood. Generally, zonisamide will cause this condition early in treatment if it is going to occur at all, but it may develop at any time during treatment. Symptoms of metabolic acidosis are; breathing fast (hyperventilation), fatigue, and loss of appetite. More severe symptoms and risks of this condition include symptoms include an irregular heart beat, unconsciousness, and death.

Placebo

There are approved medications for the treatment of alcohol dependence and they include disulfiram, naltrexone (oral and intramuscular) and acamprosate. However, all have potential limitations, including low patient acceptability (disulfiram), modest efficacy (naltrexone), high cost and poor acceptance in treatment programs (IM naltrexone) (Petrakis et al 2003), and questionable efficacy (acamprosate). Nevertheless, in accordance with IRB policy, the alternatives to participation will be clearly described to potential veterans and those that would prefer to take these medications will be referred to an appropriate facility. Additionally, all efforts will be made to monitor adverse consequences, and to withdraw veterans from the study if clinically appropriate.

CPT

Previous research shows that PTSD symptoms may increase somewhat during the early part of CPT-C. This is expected because participants are thinking and talking more about their traumatic experience(s). However, in most instances this is a transient effect. If there is an increase in PTSD symptoms participants may receive additional support. They will be provided with a wallet card that has contact information of their clinician, and will be encouraged to call their clinician for assistance.

Venipuncture and Urine Collection

The risks of blood drawing include pain, bruising, blood clots and rarely infection. The risks are substantially decreased when performed by experienced personnel using good clinical techniques. Urine specimens are collected primarily as safeguards to veterans and should add no risks other than those normally associated with these procedures.

Measures to minimize risks

As required by the VA and Yale IRB there is a clear and detailed plan for monitoring the safety of veterans participating in this study. This protocol follows the standard VA and Yale IRB format for reporting any adverse event to the IRB and other researchers, which includes a grading system to determine if an adverse event is related to the study medication, and its severity. In addition, the PI ([name]) will conduct a review of all adverse events upon completion of each study veteran as well as the frequency and severity of the adverse events on a quarterly basis. Frequent (weekly and more if needed) monitoring and assessment of subjects by the research team will help ensure safety and adequate management of adverse events. Adverse events will be monitored and tracked, recorded, and reported as required to the IRB, and other oversight entities if required. Strict separation of research and clinical components of the study will help to reduce bias from such sources as patients wanting either to deny continued problems, and/or to please the treatment team. Multiple sources of information will be used to detect such biases as it may occur.

This study will also be reviewed by the Monitoring Board associated with the Center for Translational Neuroscience of Alcoholism (CTNA) (a NIAAA funded grant, PI= [name]) on a twice yearly schedule. The Data Safety Monitoring Board (DSMB) of the CTNA has

procedures that follow the National Institutes of Health (NIH) guidelines, and consists of the following individuals. [name], PhD of Brown University, an expert in the clinical neuroscience of alcoholism and a practicing psychiatrist is the head of the Committee. The other members include [name] of Decision Sciences Institute, [name] of the University of Oregon Health Center, [name] Professor of Applied Ethics in the department of Philosophy at Fairfield University and [name], Professor of Psychiatry at Yale University and Lecturer, Yale Law School.

In addition, [name] will serve as the Research Monitor and her functions will include the following:

1. observing recruitment and enrollment procedures and the consent process for individuals, groups or units,
2. overseeing study interventions and interactions,
3. reviewing monitoring plans;
4. overseeing data matching, data collection, and analysis
5. discussing the research protocol with the investigators, interview human subjects, and consult with others outside of the study about the research;
6. shall have authority to stop a research protocol in progress, remove individual human subjects from a research protocol, and take whatever steps are necessary to protect the safety and well-being of human subjects until the IRB can assess the monitor's report.
7. shall have the responsibility to promptly report their observations and findings to the IRB or other designated official.

As noted above, precautions for pregnant or reproductive age women are in accordance with VA and Yale IRB (HIC) requirements and this will be monitored as part of the DSMP. All adverse events in the taper/follow-up time-period will be reported to the IRBs, with serious adverse events being reported within 48 hours. If during the study or at the time of tapering off of the medication the participant requires more significant care for worsening of either drinking or other psychiatric symptoms he/she may be referred to: 1) outpatient services, specific for either PTSD and/or drinking (evidence based therapy, pharmacotherapy, substance abuse services), 2) acute inpatient unit, 3)day program, 4) residential program, 5) psychiatric emergency services.

All unanticipated problems involving risk to subjects or others, serious adverse events related to participation in the study and subject deaths related to participation in the study will be promptly reported by [contact]), by email ([contact]), or by [contact]) to the USAMRMC, Office of Research Protections, Human Research Protection Office. A complete written report will follow the initial notification. In addition to the methods above, the complete report will be sent to the U.S. Army Medical Research and Materiel Command, ATTN: MCMR-ZB-PH, [name].”

XIV. Benefits

This study will not be of direct benefit to subjects. However this study may be of help in the future to veterans who have comorbid AD and PTSD.

XV. Compensation

All veterans will be compensated for their participation. Veterans will receive a check/direct deposit payment at the end of each appointment: \$20 at the screening appointment, \$30 baseline appointment, \$30 at each weekly appointment, \$50 for the Week 12 assessment, \$30 for the Week 13 assessment, \$30 for the Week 14 assessment, and \$30 for the follow-up. Veterans can receive up to a total of \$520 if attending all scheduled visits.

XVI. Confidentiality

All reports generated from this study will not contain any identifying information about the participants. Research records are coded only by a number, and are stored in locked cabinets. Consent forms, release of information forms, and research nurse medical charts will be kept locked in a place separate from subject data collection forms. Subjects will be informed that medical evaluations, including physicals, EKGs, and urine/blood tests will be administered through the hospital and will become part of their permanent record. Finally, subjects will be informed that a hard copy of the consent form will be placed in their paper record. An electronic progress note citing their participation in this research study will be entered in their electronic chart upon entry into and exit from, the study.

Accurate and complete study records will be maintained and made available to representatives of the U.S. Army Medical Research and Materiel Command. These representatives are authorized to review research records as part of their responsibility to protect human research volunteers. Research records will be stored in a confidential manner so as to protect the confidentiality of subject information.

XVII. Literature Review

Ahrens, J and Rexford, L (2002). "Cognitive Processing Therapy for Incarcerated Adolescents with PTSD." *Journal of Aggression, Maltreatment & Trauma* 6(1): 201-16.

Akuchekian, S and Amanat, S (2004). "The Comparison of Topiramate and Placebo in the Treatment of Posttraumatic Stress Disorder: A Randomized, Double-Blind Study." *Journal of Research in Medical Sciences* 9(5).

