I. Protocol Information

Title: Zonisamide in addition to Enhanced Cognitive Processing Therapy-C (E-CPT-C) for Veterans with PTSD and Comorbid Alcohol Dependence

Proposal number: 102450059

Phase: II

Version/Date of Protocol: 11/24/15

II. Sponsor Information

This study is being sponsored by the Department of Defense (DOD) Telemedicine and Advanced Technology Research Center (TATRC).

III. Principal Investigator's Information

P.I. Name: [name].

Research Institution: Yale University/Veterans' Affairs Connecticut Healthcare System

[contact] [name]

[contact]

Email: [contact]

IV. Roles and Responsibilities

The P.I. will be responsible for making eligibility/termination decisions, obtaining informed consent, evaluating adverse events, making data entries or corrections, and seeing protected health information (PHI). Provide oversight on all aspects of the research study.

The Study Coordinator will be responsible for study recruitment, collection of the assessments, data management, and regulatory correspondence. Assist in preparing data for presentations and publications. Prepare records for the Data Safety Monitoring Board.

Co-investigators will be responsible for medical coverage, medical supervision and physical examinations. They will also be part of the data analysis, summary reports, interpreting results, preparation of scientific manuscripts.

Study nurses will be responsible for meeting with subjects weekly to follow their response and side effects to the medication. Maintain all appropriate nursing documentation according to the Good Clinical Practice and VA Connecticut Healthcare System Nursing Procedures.

Study clinicians will be responsible for conducting the E-CPT-C therapy.

Laboratory Technician will be responsible for running EtG and urinary cotinine levels and will coordinate about issues related to organizing sample collection.

V. Site Information

All aspects of the study will be conducted at the West Haven VA Hospital. [name]

VI. Study Information

This study is designed to determine if the drug Zonisamide is more effective than placebo in decreasing alcohol use and PTSD symptoms when used in combination with Enhanced Cognitive Processing Therapy (E-CPT-C) in veterans with Post-Traumatic Stress Disorder (PTSD) and comorbid alcohol dependence.

VII. Study Design

Background

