The study we are proposing has the potential to influence the way treatment of PTSD and alcohol dependence is delivered across the VA Healthcare Administration (VHA) and the Department of Defense. The population we are going to study are veterans that have served in the military and may have participated in past or current military conflicts. All participants will have current Diagnostic and Statistical Manual of Mental Disorder, 4th Edition (DSM-IV) diagnoses of PTSD and alcohol dependence, two of the most common diagnoses among veterans particularly those who have experienced combat.

Currently Cognitive Processing Therapy (CPT) and CPT-C (CPT without imaginal exposure) are being rolled out nationally in a large dissemination project by the Veterans Health Administration (VHA) and the Department of Defense (DoD) as one of two gold standards for the treatment of PTSD. Unfortunately, neither CPT nor CPT-C address the needs of patients with comorbid alcohol dependence. Our study will further test a newly developed enhanced CPT-C (E-CPT-C) for veterans with PTSD and comorbid alcohol dependence. The study will test E-CPT-C in combination with a new pharmacotherapy for veterans with PTSD and alcohol dependence. Zonisamide is a promising new pharmacotherapy for alcoholism. If effective, it has the potential to be prescribed as a first line medication for alcoholism for veterans.

Overview:

This is a randomized, controlled trial with 100 veterans diagnosed with PTSD and comorbid alcohol dependence. Veterans will be randomized to receive either zonisamide (400 mg) or placebo for 12 weeks in a double blind fashion. Randomization will be done using 3:1 ratio and will be performed by our research pharmacy using a random assignment in blocks of 4- 3 will be assigned to active medication and 1 to placebo.. Medication will be titrated over a 6 week titration phase followed by a 6 week treatment phase. All veterans will receive E-CPT-C therapy for the 12 weeks of treatment; E-CPT-C will be provided by trained and qualified clinicians with extensive experience providing E-CPT-C. Veterans will be recruited primarily through advertisement, but also through the clinical facilities at the VA and from other collaborators.

Experimental subjects:

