Fifty veterans aged 21- 65 years old, with a current Diagnostic and Statistical Manual-IV, TR (DSM-IV) diagnosis of PTSD, assessed by the Structured Clinical Interview for DSM Disorders (SCID) & Clinician Administered PTSD Scale for DSM-IV (CAPS), and alcohol dependence (assessed using Structured Clinical Interview for DSM-IV) will be enrolled.

Study Procedures:

Overview: After signing informed consent, participants will undergo an initial assessments and screening. The screening will consist of careful psychiatric and medical evaluation that will also include screening for a veteran's potential to develop alcohol withdrawal. Those veterans who need treatment for alcohol withdrawal will be referred to our detoxification clinic as a first line of treatment. Initial assessments will include a careful diagnostic evaluation completed by highly trained and experienced research personnel, as well as collection of baseline assessments of alcohol use, PTSD symptoms and other characteristics. Veterans will be randomized to zonisamide 400mg or placebo for 12 weeks. The dose and titration schedule for zonisamide was selected based on data from clinical trials and is consistent with the recommended dosing schedules. All veterans will also be enrolled in E-CPT-C therapy. Assessments will occur weekly. At each visit veterans will have an interview with a member of the research staff whom is not providing the E-CPT-C training, receive a supply of medication, and complete self-report measures. Veterans will be compensated for their participation using a schedule outlined below. There will be one follow up session 3 months after completion of treatment.

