Initial Assessments/Screening: In order to qualify for participation, veterans will complete the following: (1) Diagnostic interview with the Structured Clinical Interview for DSM Disorders (SCID I), a comprehensive psychiatric interview schedule designed to assess psychiatric disorders in adults (First et al 1996). The SCID interview schedule covers the major Axis I psychiatric disorders defined in DSM-IV. The SCID permits comprehensive assessment of substance use as well as comorbid psychiatric disorders. (2) Drinking patterns will be assessed using The TLFB method (Sobell and Sobell 1992). This will allow documentation of the degree and frequency of daily alcohol consumption and smoking pattern. (3) PTSD symptom will be assessed using the Clinician Administered PTSD Assessment (CAPS), and (4) Veterans will have a medical history and physical examination by one of the investigators, blood tests (including SMAC-20, serum gamma-glutamyl transferase (γ -GGT), CBC with differential, thyroid function tests, and TSH), urinalysis, urine toxicology, and an electrocardiogram (EKG). It is anticipated, however, that

mild to moderate elevations in liver function tests will be common in alcohol dependent subjects. Veterans with LFT abnormalities that do not exceed 3 times normal values will be included.

Study Treatments:

Medication Treatment: Zonisamide, (target 400 mg) will be titrated upward over 6 weeks. Dosing will be given once daily and veterans on placebo will be given identical number, color and consistency of capsules as those on active medication. Below is the proposed dosing schedule, although we will make adjustments if side effects occur:

Zonisamide 400mg/day

Week 1:	Days 1-7	ZON 100mg, +	= TOTAL 100mg
Week 2:	Days 1-7	ZON 200mg, +	= TOTAL 200mg
Week 3:	Days 1-7	ZON 200mg, +	= TOTAL 200 mg
Week 4:	Days 1-7	ZON 300mg, +	= TOTAL 300 mg
Week 5:	Days 1-7	ZON 300mg, +	= TOTAL 300 mg
Week 6:	Days 1-7	ZON 400mg, +	= TOTAL 400 mg
Week 7-12:	Days 1-42	ZON 400mg, +	= TOTAL 400 mg

Week 13-14: TAPER by 100 mg every 3 days for a total of 2 weeks.

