Pharmacy Procedures: Veterans will start study medication on the day of randomization. The authorized prescribers of zonisamide for the study are [name]., [name]., [name]., [name] and [name]. The research pharmacy will dispense the medications and will take back any medications that are not used, keeping a record of used and unused medications. In addition to that we will record at each visit that the medication was dispensed, the number of pills, and if any medications were missed during the previous week. The study nurse will administer the first dose and veterans will be asked to stay in the research office for approximately 1 hour after the dose is administered. The zonisamide will be started at a low dose (see schedule above) and titrated upward based on the outlined schedule. The target dose for the zonisamide will be 400mg/day. Veterans will meet with the study nurse every visit to discuss any side effects of the medications, and will do study assessments with the research personnel. If veterans experience side effects that cannot be managed by adjustments in the timing of the medication (i.e. taking at bedtime, etc.), veterans may have their medication titration either held or the medication dose may be decreased. The study psychiatrist (who is blinded to the condition, but may request a dose decrease to the next lowest dose) and the research pharmacist (who is not blinded, but who has no contact with the veteran) will do this. The psychiatrist will contact the pharmacist and request a decrease in dose. In case of an emergency, the blind will be broken and appropriate medical care initiated. Since this is a pilot study, the proposed dosing schedule will be evaluated and may be modified depending on the findings from the pilot study.

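### Fixed blocks of 4 with one placebo let a single placebo code break identify three other veterans as active; pharmacy-held varying block sizes would reduce this low-impact leak at little cost

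*Combined protocol and SAP*

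**What the plan says.** The Overview in Section VII describes a double-blind trial randomized 3:1 by the research pharmacy, "using a random assignment in blocks of 4- 3 will be assigned to active medication and 1 to placebo". It names no other block size and no stratification, and it does not say that the block size is withheld from staff.

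Three other statements bear on whether a block can be reconstructed:

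- Section V: "All aspects of the study will be conducted at the West Haven VA Hospital". With no stratification described, there is one enrolment stream.
- Pharmacy Procedures: "Veterans will start study medication on the day of randomization". The study nurse gives the first dose, so first-dose dates show staff the order.
- Pharmacy Procedures: "In case of an emergency, the blind will be broken and appropriate medical care initiated". The text does not say how often this is expected or who is told the result.

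The plan also contains real safeguards:

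- Under Medication Treatment, "veterans on placebo will be given identical number, color and consistency of capsules as those on active medication".
- Under Pharmacy Procedures, the unblinded pharmacist does not meet the veterans.
- The Study Procedures overview provides for "an interview with a member of the research staff whom is not providing the E-CPT-C training". The E-CPT-C section adds that another team member rates PTSD and alcohol symptoms, so that the ratings are unbiased.
- Under EtG Storage and Analysis, the EtG readers do not know the treatment.
- Under Measures to minimize risks, research and clinical work are kept apart to reduce bias.

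**The concern.** With one block size and one placebo per block, a code break can tell staff about veterans other than the one concerned. The protocol itself states the block size and composition, so a reader who knows the order of enrolment needs nothing from the pharmacy list to work out the rest of the block.

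Two things could follow. Someone who rates or manages the block-mates might be influenced by knowing their treatment. And if the break comes before the block has filled, the remaining assignments become more predictable to whoever decides eligibility.

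**Working it through.** **Inputs from the documents.** Ratio 3:1, blocks of 4 (3 active, 1 placebo) and N=100 (Section VII, Overview; Section IX also gives 100). The Experimental subjects paragraph gives 50, a discrepancy that does not affect the argument.

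**The plan's own figures.** 100/4 = 25 blocks, so 25 × 3 = 75 active and 25 × 1 = 25 placebo. Before any break, each veteran is active with probability 3/4 = 0.75.

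**Fixed blocks of 4, order known.**

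- Placebo revealed: no placebo is left among the other three, so each is active with probability 3/3 = 1.00.
- Active revealed: two active and one placebo remain, so each is active with probability 2/3 = 0.667.
- Placebo revealed, block boundaries not known: the next veteran shares the block with chance 3/4, giving 3/4 × 1 + 1/4 × 0.75 = 0.9375.

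**Exposure.** One placebo break exposes at most 3 of 75 active veterans (4%) at N=100, or 3 of about 37.5 (8%) at N=50.

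**Varying sizes.** The menus 4/8 and 4/8/12, with sizes equally likely, are assumptions; 3:1 requires multiples of 4. Every boundary then falls on a multiple of 4, so an observer can still line up the fours. In the long run a given four lies in a block of size s with chance s divided by the sum of the sizes. After a placebo is revealed, each of the other three in that four is active with probability:

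- 4/8: 1/3 × 1 + 2/3 × 6/7 = 0.905
- 4/8/12: 1/6 × 1 + 1/3 × 6/7 + 1/2 × 9/11 = 0.861

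An exact calculation over 100 positions gives averages of 0.905 (range 0.893 to 0.929 by position) and 0.862 (0.855 to 0.892). No other veteran is identified with certainty.

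The chance that all three are active is 1.00 now. It becomes 1/3 + 2/3 × (6·5·4)/(7·6·5) = 0.714 with 4/8, and 1/6 + 1/3 × 4/7 + 1/2 × (9·8·7)/(11·10·9) = 0.612 with 4/8/12.

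**Price in balance at N=100.** The placebo count departs from 25 only if enrolment stops inside a block.

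- 4/8: a boundary falls at veteran 96 with long-run chance 1/1.5 = 2/3, and the next block is an 8 with chance 1/2, so the last block is cut in half with chance 1/3. Half of an 8 holds 0 or 2 placebos with chance 6/28 each. The chance of 24 or 26 is 1/3 × 12/28 = 0.143.
- 4/8/12: simulation of 40,000 lists gave 25 in 76.4%, 24 or 26 in 23.1% (11.5% + 11.6%), and 23 or 27 in about 0.5%.

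For 24 placebo and 76 active, the standard error of a difference in means changes by √(1/24 + 1/76) / √(1/25 + 1/75) = 1.014, a rise of 1.4%.

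**The case against.** The strongest case against reporting this is that the chain is long. There must be an emergency break. The veteran must be on placebo, which is 1 in 4 if breaks are unrelated to arm. Someone must reconstruct the block, and the knowledge must reach a person who rates or manages the block-mates while there is still something to influence. Ratings made before the break are untouched. The independent-assessor arrangement and the separation of research from clinical work are aimed at that last step. The primary drinking measures are self-reported on the TLFB, and the clinician-rated CAPS serves an exploratory aim. The remedy is also partial: with 4/8 blocks a block-mate is still about 0.91 likely to be active.

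All of that stands, and it is why the impact is rated low. It does not remove the deduction itself, which is exact and follows from wording that the protocol need not contain.

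A reader might infer more than the documents support:

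- **That the P.I. would be told and would act on it.** Section IV says "The P.I. will be responsible for making eligibility/termination decisions, obtaining informed consent, evaluating adverse events, making data entries or corrections", so the role is broad. No section says that this role, or any other, is told a revealed code.
- **That the treatment estimate would be biased by some stated amount.** Any such figure needs an assumed rating bias and presupposes a placebo break. The documents supply neither a rating bias nor a break rate.
- **That assignments become more predictable only after a placebo is revealed.** An active reveal in an unfilled block also shifts the remaining places, from 0.75 to 0.667.
- **That varying block sizes would close the leak.** They lower the certainty, but it stays above 0.75.

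**Conclusion.** The point holds as a cheap improvement of low impact; the plan is not wrong as it stands. One placebo code break, with enrolment order known, raises the probability that each of three block-mates is active from 0.75 to 1.00. Any break before a block fills makes the remaining assignments somewhat more predictable. At most 3 of 75 active veterans are exposed per placebo break at N=100.

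This rests on reading the Overview as one block size throughout, on a single unstratified list, and on order being visible from start dates. The existing safeguards make an effect on outcomes unlikely, and the documents do not allow its size to be computed.

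**What to change.** For blocks not yet opened, have the research pharmacy draw permuted blocks of randomly varying size at the same 3:1 ratio, for example 4 and 8, or 4, 8 and 12. In the Overview of Section VII, delete the block size and say instead that the sizes vary at random and are held by the research pharmacy.

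The cost is one new list and a minor amendment with its ethics review; no extra veterans are needed and the ratio does not change. The placebo count would be one away from 25 in about 14% (4/8) or 23% (4/8/12) of lists at N=100, raising the standard error by about 1.4% when it is one short. Larger blocks hide more but balance less tightly. Blocks of 4 already opened stay deducible.
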